12.6 PREGNANCY AND IN UTERO DRUG EXPOSURE

However, **all pregnancies that are diagnosed up to M3 FU visit** or up to 4 weeks after the last IMP administration for subjects prematurely terminating the study must be recorded using the **Pregnancy Surveillance Form (PSF) – Part I** (History and Start of Pregnancy; PSF-part I), provided by the sponsor (or delegate) at the beginning of the study.

Initial reporting of pregnancies:

Subjects who become pregnant during the study Treatment Period will be immediately withdrawn from the IMP treatment.

The Investigator must notify the sponsor in an expedited manner (same as SAE reporting) of any pregnancy occurring during the above-mentioned period, by completing the **PSF-part I**.

This form should be sent to ObsEva's Representative for Pharmacovigilance as per the same procedures and timelines described for SAE Urgent Reporting in section 12.3.2. This form should be accompanied, as needed, by copies of the eCRF Medical History, Previous and Concomitant Therapy and the Exit Form.

Follow-up of pregnancies:

The Investigator must actively follow-up, document and report to ObsEva's Representative for Pharmacovigilance the progress by **tri-monthly updates up to the final outcome of the pregnancy** using the **Pregnancy Surveillance Form – Part II**: (Course of Pregnancy; PSF-part II). If the subject can no longer be reached (lost to follow-up), documentation of the non-response/contact with two phone calls and a letter (certified with return receipt) are required.

Pregnancy outcomes are not recorded in the eCRF unless considered AEs.

Pregnancy outcomes must be reported to ObsEva's Representative for Pharmacovigilance by completing the **Pregnancy Surveillance Form – Part III**: (Course and Outcome of Pregnancy; PSF-part III). Timelines vary according to the nature of the pregnancy outcome:

- For normal outcomes, ObsEva's Representative for Pharmacovigilance should be notified within 45 days of birth/delivery.
- For abnormal outcomes, the fully completed form must be sent to ObsEva's Representative for Pharmacovigilance according to the same procedures and timelines described for expedited AE reporting in section 12.3.2 (within 24 hours of awareness of this outcome). An SAE Report form should be completed in addition to the PSF-part III if the subject sustains an event meeting seriousness criteria (e.g. abnormality for the pregnancy (spontaneous abortion, stillbirth) or abnormality for the birth itself (e.g. prolongation of hospitalization due to caesarean section complications). In case of congenital malformation or birth defect of the child, a SAE form for the child should be completed in addition to the PSF-part III (Subject identifier = Subject ID – 1 for a singleton neonate).

13 DATA ANALYSIS AND STATISTICS

13.1 TEST OF HYPOTHESES

All statistical hypothesis tests and confidence intervals will be two sided. To maintain an overall type I error rate of 0.05, as there are two linzagolix versus placebo comparisons, Bonferoni corrected p-values will be produced (raw p-values will be multiplied by two prior to comparing to 0.05), along with corresponding 97.5% confidence intervals.

The two co-primary efficacy endpoints will be clinically meaningful reduction (see section 13.5.2) over the last 28 days of randomized treatment up to the Month 3 visit (the 4-week period preceding Month 3 visit) from baseline in the mean daily assessment of DYS and of NMPP measured on a VRS, along with a stable or decreased use of analgesics for EAP.

The primary objective will be assessed by testing the following two-sided hypotheses for each co-primary endpoint, for each linzagolix group versus placebo separately:

Null hypothesis (H0): There is no difference in the odds of subjects meeting the primary endpoint for the active treatment group compared to placebo, that is, the odds ratio (OR) equals 1.

$$H_0: OR = 1$$

Alternative hypothesis (H1): There is a difference in the odds of subjects meeting the primary endpoint for the active treatment group compared to placebo, that is, the OR is not equal to 1.

$$H_1: OR \neq 1$$

Where odds are equal to the proportion of subjects meeting the endpoint divided by proportion of subjects not meeting the endpoint.

Each linzagolix group will need to demonstrate a statistically significant difference for both co-primary endpoints in order for the group to be considered more efficacious than placebo, thus maintaining an overall type I error rate of 0.05.

For each linzagolix group that is statistically significantly more efficacious than placebo for the co-primary endpoints, a fixed-sequence testing strategy shall be used within the group to test the ranked secondary endpoints as ordered in Section 7.1.2.1, so as to maintain the family-wise type I error rate. That is, the comparison for each linzagolix group versus placebo for each ranked endpoint will only be declared statistically significant different if the raw p-value multiplied by two is less than or equal to 0.05 for that endpoint and for all preceding endpoints for that dose versus placebo.

Response rates for DYS and NMPP pain at each visit will be analyzed to evaluate the changes in pain over time, with nominal bonferroni corrected p-values used in the comparisons of treatment groups at each visit. These are supportive analyses and will primarily be considered as descriptive. The analyses do not form part of the fixed-sequence strategy being used for the ranked secondary endpoints and will not be fully controlled for an overall type I error rate. However, to maintain consistency with the primary and secondary analyses, Bonferroni corrections will be used due to there being two linzagolix versus placebo comparisons for each endpoint / time point.

13.2 SAMPLE SIZE

The planned sample size for this study is 150 subjects per treatment group (450 subjects in total).

An overall two-sided type I error of 0.05 will be used. As there are two linzagolix versus placebo comparisons, Bonferoni corrected p-values will be produced (raw p-values will be multiplied by two prior to comparing to 0.05). The planned sample size takes into account the hierarchical, fixed sequence testing of the ranked secondary endpoints as well as the co-primary endpoints. The assumptions used for the sample size calculations are based on analyses of clinically meaningful reduction in pain with a stable or decreased use of analgesics from the Phase 2b Edelweiss study. Calculations were performed using East® 6.5 software.

One hundred and fifty (150) subjects per treatment group will provide a power greater than 95% to reject the null hypothesis for both co-primary endpoints for either treatment group, assuming a placebo response rate of 14.6% and an active treatment response rate of 48.6% (75 mg, Edelweiss result) or 64.7% (200 mg, Edelweiss result) for DYS, and a placebo response rate of 18.8% and an active treatment response rate of 42.1% (75 mg, Edelweiss result; the response rate for 200 mg in Edelweiss was lower but was inconsistent with the other doses and also the other timepoints for the same dose and so has not been used) for NMPP. In addition, 150 subjects per treatment group provides 85% power to reject all the ranked secondary endpoints based on the observed results from the placebo and 200 mg treatment group in the Edelweiss study.

The values used for the sample size calculations assume that this is what would be seen on average when under treatment including taking into account any subjects who might withdraw from treatment early and therefore the calculations do not need to be further adjusted for dropouts.

13.3 RANDOMIZATION

Randomization will be performed via a centralized IWRS. Subjects will be randomized on Day 1 to one of three treatment groups in a 1:1:1 ratio for linzagolix 75 mg, linzagolix 200 mg with ABT and placebo.

Subjects will be randomized into permuted blocks of a pre-determined length.

Subjects participating in the extension phase and who are in the placebo treatment group will be randomized at Month 6 visit to either linzagolix 75 mg or linzagolix 200 mg with ABT in a 1:1 ratio. Subjects participating in the extension phase and who are in the linzagolix treatment groups will remain on the same dose that they were taking at the end of Month 6 and will undergo a dummy randomization in order to maintain the blind.

13.4 ANALYSIS SETS

The following data sets will be used for the statistical analysis:

1. **Safety Set:** All randomized subjects who received at least one dose of double-blind study drug irrespective of the treatment received. Subjects will be analyzed according to treatment received.

2. **Full Analysis Set (FAS):** All randomized subjects who received at least one dose of double-blind study drug irrespective of the treatment received. This is the same as the Safety Set, but for the FAS subjects will be analyzed according to randomized treatment.
3. **Per Protocol (PP) Set:** All randomized subjects who completed the six months of treatment excluding those identified as having major protocol deviations that could potentially affect the efficacy assessments up to Month 6. Subjects will be analyzed according to randomized treatment.
4. **Follow-up (FU) Set:** All randomized subjects who completed the six months of treatment and entered the drug free follow-up period. Subjects will be analyzed according to randomized treatment.
5. **Pharmacokinetic (PK) Set:** all subjects who received active study medication, had no major protocol deviations impacting PK and with available PK data.

Individual data points may also be excluded from the analysis sets. Rules for such exclusions will be described in the statistical analysis plan (SAP), including, where appropriate, time windows for various safety and efficacy analyses. In general, analyses of efficacy will be conducted using the FAS and PP sets, analyses of safety will be conducted using the Safety Set and analyses of PK will be conducted using the PK Set.

A sub-group analysis will be performed for the secondary endpoint of dyspareunia as described in Section 13.5.3.5. Additional pre-planned sub-group analyses will be described in the SAP.

13.5 DATA ANALYSIS

More details of the proposed statistical analyses will be documented in the SAP, which will be written following finalization of the protocol and prior to the blinded responder threshold analysis of the Month 3 data. The SAP will then be updated prior to unblinding and analysis of the data up to Month 6, in order to incorporate the results of the blinded responder threshold analysis.

For continuous data and for ordered categorical data, if appropriate, the number of non-missing observations, mean, standard deviation, median, first and third quartiles, minimum and maximum will be calculated, including for change from baseline when applicable. The baseline mean will be calculated for all subjects based on the FAS. A baseline mean will also be calculated for each visit using the baseline data for the subset of patients who attend that visit, such that the same subjects contribute to the mean for the visit and the mean for the corresponding baseline values. Summary statistics will be based primarily on non-missing values. For ordered categorical data and nominal data, absolute counts and relative frequencies (in %) will be calculated. As appropriate, time windows for various safety and efficacy analyses will be defined in the SAP.

This study will be conducted at approximately 100 study sites, resulting in only a few subjects per site on average. Subjects from all sites will be pooled and no adjustment for sites will be carried out in the statistical analyses.

The number of subjects randomized, who received at least one dose of study drug, who completed the study and who prematurely discontinued will be calculated overall and for each site by treatment group, as well as for all subjects combined. Premature discontinuation of study drug will be summarized for

each treatment group, as well as for all subjects combined, with frequencies and percentages overall and by reason for discontinuation for all randomized subjects.

Raw and derived data will be listed.

13.5.1 Baseline Assessment

Descriptive statistics will be performed on relevant screening and baseline data (i.e. data collected prior to the treatment administration) and on demographic characteristics for each treatment group and overall. There will be no formal comparison of baseline data, that is, no statistical hypothesis testing.

13.5.2 Primary Efficacy Analysis

The primary efficacy analysis aims to estimate the effect of linzagolix versus placebo on DYS and NMPP over the last 28 days up to and including the Month 3 visit or, for subjects who discontinue randomized treatment prior to the Month 3 visit, over the last 28 days of randomized treatment. Use of analgesic medication for EAP will be included in the responder definitions. A responder for each of the co-primary endpoints needs to demonstrate both a reduction in pain (DYS or NMPP, depending on the endpoint) and a stable or decreased use of analgesics for EAP. Anyone who does not meet both of these criteria will be defined as a non-responder.

The primary efficacy analysis will be conducted using the FAS.

For each of the co-primary endpoints, the criterion for defining a subject as a responder over the last 28 days of randomized treatment up to the Month 3 visit will include a reduction of X or greater from baseline in pain, where X will be determined using appropriate anchors as described below, as well as a stable or decreased use of analgesics for EAP.

Mean pelvic pain scores for DYS and for NMPP will be calculated by averaging over the corresponding 28 calendar days immediately prior to and including the day of the Month 3 visit. DYS will use days with uterine bleeding, defined as those days on which the subject records any uterine bleeding or spotting in the subject eDiary; NMPP will use days with no uterine bleeding. If a subject's mean score for DYS is undefined numerically because her daily eDiary reports indicate that she did not experience uterine bleeding on any days during the 28 calendar day time period, then the mean score for DYS will be set equal to zero (which reflects the absence of any DYS during that reporting time period). For subjects who discontinue treatment prior to Month 3, the last available observations prior to discontinuation will be used, in order to estimate the treatment effect of while under treatment, that is the 28 calendar days immediately prior to and including the last dose date (or fewer if treatment is stopped less than 4 weeks after randomization). The baseline mean overall pelvic pain scores for DYS and NMPP will be calculated by averaging over the two complete menstrual cycles during screening, which may not be exactly 28 days each. For both DYS and NMPP, responses of "None," "Mild," "Moderate," and "Severe" will be assigned a score of 0, 1, 2, and 3, respectively.

For the assessment of a stable or decreased use of analgesics for EAP, the analgesic use for any defined period will be based on the mean of the total pill count for each class of rescue analgesics (endometriosis-associated). The total pill count for each class of rescue analgesic is the sum of the pill count of the corresponding class of rescue analgesic, as reported in the eDiary during the time period of interest. The baseline analgesic use will be calculated as the mean of daily pill count of analgesics over the two complete menstrual cycles during screening. For purposes of determining a stable or decreased use of

analgesics, the averaging will be done over the same calendar days as used for the pelvic pain scores. The evaluation of a stable or decreased use of analgesics will be done per the specification in Appendix O.

The analysis of each co-primary endpoint will be conducted using a logistic regression model, with treatment group as the main effect (three values) and including the baseline pain score as a covariate. Individual linzagolix versus placebo treatment group comparisons will be made using the same logistic regression model.

Responder threshold analysis:

For each of the co-primary endpoints, the criterion for defining a subject as a responder over the last 28 days of randomized treatment up to the Month 3 visit will be a reduction of X or greater from baseline in pain. The threshold for response in the responder analysis (i.e., the value of X) will be chosen to represent a clinically meaningful reduction in pain and may not be the same for each endpoint. The threshold will be determined based on separate analyses of overall mean change using the mPGIS at Month 3 as an anchor. A 2-point improvement in the mPGIS will be used to define responders for the primary analysis. Response categories of “very mild” and “mild” will be collapsed into one category prior to the analyses. Monthly questions specific to DYS, NMPP, overall pelvic pain, dyschezia, dyspareunia and daily function will be used as separate anchors. PGIC as an anchor, Cumulative Distribution Function (CDF) and Probability Density Function (PDF) curves, and Receiver Operating Characteristic (ROC) analyses will be used as supportive analyses. The thresholds have been estimated in an analysis of DYS and NMPP data from the Phase 2b Edelweiss study and will be re-estimated in this study, calculated based on the blinded Month 3 data. As with the under treatment efficacy analysis, for subjects who discontinue treatment prior to Month 3, the 28 calendar days immediately prior to and including the last dose date will be used, along with the closest time matched PGIS and PGIC. The final response thresholds taking into account the previous estimates from phase 2b will be included in the final SAP prior to breaking the blind after Month 6. Based on the results from the Phase 2b Edelweiss study, it is expected that the responder threshold will be in the range of a 0.7 to 1.25 point (40% to 50%) reduction in pain in the 4-point VRS for a 2-point improvement and a 0.25 to 0.75 point (20% to 30%) reduction in pain in the 4-point VRS for a 1-point improvement. The numerical thresholds for DYS are expected to be larger than those for NMPP.

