13.5.8 Missing Data

Summary statistics will be based primarily on non-missing values. The planned statistical analyses aim to estimate the efficacy of linzagolix versus placebo whilst under randomized treatment and therefore lack of data after treatment discontinuation will not be considered as missing for these analyses.

Subjects who cannot be assessed as responders or not for the co-primary efficacy endpoints, e.g. due to lack of enough on treatment pain data will be considered as non-responders. In addition, for endpoints assessing the numeric change from baseline, such subjects will be assigned a change from baseline of zero. It is expected that very few subjects will be affected by these rules.

As additional analyses, in order to estimate the effect of treatment policy, a reference based multiple imputation approach will be used for the co-primary endpoints for subjects who discontinue the study early under the assumption that the efficacy of the linzagolix treated subjects gradually transitions to that observed in the placebo subjects.

There may be missing data during the screening period and whilst under treatment, for example, missed days of completing the eDiary. The primary analyses will use observed data only in such cases provided that a minimum number of completed daily eDiary entries are available. This effectively assumes that the individual values such as daily eDiary assessments (observed or not) are independent of being missing.

Further details on the handling of missing values and the methods and planned sensitivity analyses to check the robustness of the analysis results under alternative assumptions with regards to missing data will be provided in the SAP.

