4.2.8. Missing, Unused, and Spurious Data

4.2.8.1. Efficacy Endpoints Missing Data

Summary statistics will be based primarily on non-missing values. The planned statistical analyses aim to estimate the efficacy of linzagolix versus placebo while under randomized treatment and therefore lack of data after treatment discontinuation will not be considered as missing for these analyses.

Subjects who cannot be assessed as responders for the co-primary efficacy endpoints, e.g. due to lack of on treatment pain data (i.e. subjects who received less than 28 days of treatment), will be considered as non-responders. In addition, for endpoints assessing the numeric change from baseline, such subjects will be assigned a change from baseline of zero. It is expected that very few subjects will be affected by these rules.

There may be missing data during the screening period and whilst under treatment, for example, missed days of completing the eDiary. The primary analyses will use observed data only in such cases provided that a minimum number of completed daily eDiary entries are available. This effectively assumes that the individual values such as daily eDiary assessments (observed or not) are independent of being missing.

Further details on the handling of missing values and the methods and planned sensitivity analyses to check the robustness of the analysis results under alternative assumptions with regards to missing data are provided in the analyses sections. As additional analyses, in order to estimate the effect of treatment policy, a reference based multiple imputation approach will be used for the co-primary endpoints for subjects who discontinue the study early under the assumption that the efficacy of the linzagolix treated subjects gradually transitions to that observed in the placebo subjects.

Missingness Assumptions:

Missing At Random (MAR): Missingness is independent of unobserved outcomes given observed data. Subjects with missing data can be modeled based on similar subjects with available data if we account in the model for relevant observed factors.

Missing Not At Random (MNAR): The probability of missingness depends on the unobserved outcome and cannot be predicted only based on observed data.

Multiple Imputation Methodology:

Multiple imputation inference involves three distinct steps:

Sponsor:	ObsEva		
Protocol:	18-OBE2109-00	18-OBE2109-003	
Document Version No.:	V5.0		

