Intercurrent events: Increased use of EAP analgesia is a non-response in the endpoint definition. Treatment discontinuations are assessed up to the time of discontinuation. Randomized treatment will be considered, regardless of lack of compliance to treatment or treatment assignment errors. The clinical question of interest is based on a while-on-treatment strategy for discontinuation and composite strategy for analgesic use. Lack of compliance to treatment and treatment assignment errors are handled using a treatment policy strategy.

The "while-on-treatment strategy" was chosen for the intercurrent event of discontinuation of treatment for the co-primary endpoints based on the recommended strategies for addressing intercurrent events in the (then draft) ICH E9 (R1) guideline.

Sponsor:	ObsEva	ObsEva		
Protocol:	18-OBE2109-00	18-OBE2109-003		
Document Version No.:	V5.0 Document Date: 13-JUN-2022			

The response to treatment prior to the occurrence of the patient discontinuing treatment is of clinical interest for a symptomatic treatment of endometriosis-associated pain. Patients and prescribers are generally interested in what happens when a patient actually takes (and can take) the treatment. This corresponds most directly to the "while on treatment" strategy for treatment discontinuation. Of note, a comparison of patient disposition and discontinuation rates will also constitute an important aspect when interpreting the study results. In addition, a "while-on-treatment" strategy for efficacy aligns with the analysis of adverse events, which are also considered while on treatment. Moreover, as endometriosis-related pelvic pain is measured repeatedly each day, the variable can be readily calculated for the 28-day period up to the point of discontinuation and the value up to the time of discontinuation can be considered to account for the intercurrent event.

For each of the co-primary endpoints, the criterion for defining a subject as a responder over the last 28 days of randomized treatment up to the Month 3 visit will include a reduction of X or greater from baseline in pain, where X was determined by a meaningful change threshold estimation using appropriate anchors as described in Section 4.6.1, as well as stable or decreased use of analgesics for EAP. Results of the meaningful change threshold estimation 4.6.1.3.

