Subjects whose response cannot be assessed for the co-primary efficacy endpoints, e.g. due to lack of on treatment pain data (i.e. subjects who received less than 28 days of treatment), will be considered as non-responders. In addition, for outputs presenting the numeric change from baseline, such subject will be assigned a change from baseline of zero. It is expected that very few subjects will be affected by these rules.

There may be missing data during the screening period and whilst under treatment, for example, missed days of completing the eDiary. The primary analyses will use observed data only in such cases, provided that a minimum number of completed daily eDiary entries are available. This effectively assumes that the individual values such as daily eDiary assessments (observed or not) are independent of being missing. Subjects who have less than the minimum number of days available will be excluded from the analysis. This is valid under the assumption that such data is MAR, conditional on the baseline value.

The required minimum number of completed daily eDiary entries will be set to 12 days of each 28-day period (two Baseline menstrual cycles and the 28-day period prior to Month 3), i.e., 43% of non-missing assessments for the primary analysis, consistent with the use of 3 days per week as the minimum number of completed diary entries as suggested in recent research ((Griffiths & al, 2018), (Cappelleri & Bushmakin, Biopharmaceutical Report, 2020), (Cappelleri & Bushmakin, Biopharmaceutical Report, 2020), (Cappelleri & Bushmakin, Biopharmaceutical Report, 2020), Cappelleri & Bushmakin, Biopharmaceutical Report, 2020), (Cappelleri & Bushmakin, Biopharmaceutical Report, 2020), completed daily eDiaries for DYS, NMPP and analgesic use.

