4.6.4. Additional Secondary Endpoints

All additional efficacy endpoints will be summarized by descriptive statistics for each treatment group, for each time point, including summaries of change from baseline when applicable. Individual linzagolix versus placebo treatment group comparisons will be made.

In general, between group comparisons for continuous endpoints will be analyzed via analysis of (co)variance. Between-group comparisons for binary endpoints will be analyzed via logistic regression. Between-group comparisons for ordinal categorical data will be analyzed using a Mantel-Haenszel test, or using Koch's method when there is also a baseline covariate.

As described in section 4.2.5 additional secondary endpoints will use Bonferroni correction for p-values of comparison of treatment groups at each visit. The analyses do not form part of the fixed-sequence strategy being used for the ranked secondary endpoints and will not be fully controlled for an overall type I error rate.

Values for all endpoints that are collected daily using the eDiary (from Section 4.6.4.1 to Section 4.6.4.18) will be based on the 28 calendar days immediately prior to and including the day of the corresponding visit or prior to and including the last treatment administration date for Month 6, or the 28 calendar days immediately prior to and including the last dose date for subjects who discontinue treatment prior to the visit in question (or fewer if treatment is stopped less than 4 weeks after first dose date), in order to estimate the treatment effect while under treatment. The last 28 days on treatment will be used at all subsequent scheduled visits for those discontinued subjects. Descriptive summaries for each 28-day period will be performed in two ways however:

- Once including only values of 28 days prior to Month X, i.e. using the last 28 days prior to Month X eCRF visit date for subjects who have not discontinued up to that month. If subjects discontinued prior to Month X the corresponding value will be missing from the summary at Month X;
- Once applying the while on treatment strategy, i.e. using the last 28 days prior to Month X eCRF visit date for subjects who have not discontinued up to that month, and for subjects who discontinued prior to Month X, the last 28 days prior to treatment discontinuation will be used. For all subsequent timepoints (Month X+1, etc.) the same last 28 days prior to treatment discontinuation will be used.

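### Women treated for fewer than 28 days fall under conflicting co-primary rules, and the SAP's non-response rule departs from its own while-on-treatment strategy without being declared

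*Protocol*

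**What the plan says.** **Protocol.** Section 13.5.2 defines the co-primary scores for early stoppers over the last 28 on-treatment days, "or fewer if treatment is stopped less than 4 weeks after randomization". Section 13.5.4 repeats that allowance for diary endpoints. The synopsis version of the co-primary rule and the responder-threshold paragraph of 13.5.2 leave it out. Section 13.5.8 adds a fallback: women who cannot be assessed "due to lack of enough on treatment pain data will be considered as non-responders", with zero change on numeric endpoints. It sets no 28-day cut-off.

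**SAP, co-primary.** Section 4.6.2.1.1 drops the shorter-window allowance, but on intercurrent events it says "Treatment discontinuations are assessed up to the time of discontinuation" and names a while-on-treatment strategy. Section 4.6.2.1.2 identifies the unassessable women as follows: "i.e. subjects who received less than 28 days of treatment), will be considered as non-responders". On numeric change, "such subject will be assigned a change from baseline of zero". Section 4.2.8.1 states the same rule for efficacy endpoints in general ("such subjects will be assigned a change from baseline of zero"). Yet 4.6.2.1.2 also summarises Month 3 change for discontinued women over their last 28 treatment days or less. It further excludes from the analysis women with fewer than 12 diary entries in the 28-day period.

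**SAP, additional secondary endpoints.** Section 4.6.4 restores the short window, "or fewer if treatment is stopped less than 4 weeks after first dose date", and carries that window to all later visits.

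**SAP, labels and declared changes.** Section 4.6.5.1 describes scoring all pre-Month 3 discontinuers as non-responders as a composite strategy, in contrast to the primary estimand. Section 5 lists one departure from the protocol's analyses, the Month 6 window. Neither it nor the version table mentions the under-28-day rule.

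**The concern.** A woman who takes drug for 20 days and completes her diary every day has on-treatment data. The protocol's detailed rule scores her. The SAP's co-primary rule fails her because of when she stopped, not because data are lacking. That is the handling the SAP itself calls composite when it applies it to all discontinuers in a supportive analysis. A reader of 4.6.2.1.1 would not know that the primary analysis mixes the two strategies.

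There is also a reproducibility problem. Two programmers working from this SAP could each defend a different co-primary status for the same woman: scored, failed or excluded. The last two differ in effect, since one keeps her in the denominator and the other removes her under a missing-at-random assumption.

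**Working it through.** **1. The rules applied to four cases.** Entries are counted within the last 28 on-treatment days.

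| Case | Protocol 13.5.2 and 13.5.8 | SAP under-28-day rule (4.2.8.1, 4.6.2.1.2) | SAP available-days text (4.6.2.1.2 summary, 4.6.4) | SAP 12-entry sentence |
|---|---|---|---|---|
| Stops Day 10, 10 entries | 10 days, or non-response if not enough | Non-responder, zero change | 10 days, below minimum | Excluded |
| Stops Day 20, 20 entries | Scored on 20 days | Non-responder, zero change | Scored on 20 days | Passes |
| Treated 60 days, 12 entries | Scored | Not affected | Scored | Passes |
| Treated 60 days, 11 entries | No minimum stated | Not affected | Below minimum | Excluded |

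The second row is the conflict with the estimand, and the first is the unresolved choice between failure and exclusion. Comparing the second and third rows shows that the rule does not track data sufficiency: 20 entries fail and 12 are scored. Reading the minimum as a count of 12 entries, a woman stopping before about Day 12 cannot reach it even with a perfect diary. The group whose status turns on the choice of rule is therefore those stopping at about Day 12 to 27.

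**2. Reproducing the stated power.** Protocol 13.2 claims more than 95% for both co-primaries with 150 per arm. Each comparison uses two-sided alpha 0.025, so z = 2.241. NMPP is the limiting endpoint: 18.8% vs 42.1%, mean 30.45%.

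Power = Φ{[d√n − z√(2p̄(1−p̄))] / √(p₁q₁ + p₂q₂)}
= Φ{[0.233 × 12.247 − 2.241 × 0.651] / 0.630}
= Φ(2.22) = 98.7%.

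DYS power exceeds 99.9% at both doses, so joint power is also 98.7%. The claim reproduces.

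**3. Effect on NMPP of forcing non-response.** Assumption: a share d of an arm is treated under 28 days and would otherwise respond at the arm's planned rate, so p becomes p(1 − d).

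| d placebo / active | Difference (points) | Odds ratio | Power |
|---|---|---|---|
| 0 / 0 | 23.3 | 3.14 | 98.7% |
| 2% / 2% | 22.8 | 3.11 | 98.4% |
| 5% / 5% | 22.1 | 3.07 | 98.0% |
| 10% / 10% | 21.0 | 3.00 | 97.0% |
| 5% / 10% | 20.0 | 2.81 | 95.3% |
| 2% / 10% | 19.5 | 2.70 | 93.9% |
| 10% / 5% | 23.1 | 3.27 | 98.8% |

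**4. Shift in the response-rate difference under separate assumptions.** Assume that 3–8% of an active arm and 3–4% of placebo stop before Day 28, and that 30–50% and 10–15% of them respectively would respond on available days. The shift is f_active × r_active − f_placebo × r_placebo.

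- Smallest: 0.03 × 0.30 − 0.04 × 0.15 = 0.009 − 0.006 = 0.3 points.
- Largest: 0.08 × 0.50 − 0.03 × 0.10 = 0.040 − 0.003 = 3.7 points.

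Steps 3 and 4 count everyone stopping before Day 28. They overstate the effect, because women stopping before about Day 12 would be non-responders under the rule recommended below as well.

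**The case against.** The sponsor has a reasonable reply. The estimand's variable is a mean over the last 28 days on treatment, and SAP 4.6.2.1.1 justifies the strategy by pointing to that 28-day period. A woman with fewer days lacks the complete variable. Protocol 13.5.8 already provides non-response and zero change for insufficient data and leaves further detail to the SAP, so the SAP could be said only to put a number on what is enough. The synopsis omits the shorter-window clause, and the SAP's co-primary definition matches it. Dosing normally starts on days 1 to 7 of menses, so DYS days in a short window come largely from that first bleed, when a drug effect is least plausible. Under the step 4 assumptions the rule lowers the treatment difference, which is conservative.

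Much of this stands. The protocol is not uniform, the zero-change rule is the protocol's own, and a short window may represent a cycle poorly. But 13.5.2 expressly provides the shorter window, a 28-day cut-off contradicts it, and the SAP itself uses available days elsewhere. If a short window is thought uninformative, that is a reason to declare a composite component, not to leave it under a while-on-treatment label. Nor is the rule always conservative: with more early stopping on placebo (10% vs 5%), the NMPP odds ratio rises from 3.14 to 3.27.

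Three stronger readings may tempt a reader, and the documents do not support them:

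- That every woman stopping before Day 28 is wrongly failed. The 12-entry minimum limits this to about Day 12 to 27.
- That her responder status differs between tables at the same visit. SAP 4.6.4.1 covers visits other than Month 3, so the same-visit clash concerns numeric change only. The same treatment days could still yield response in a 4.6.4.1 table and non-response in the primary.
- That early stopping will differ by arm and bias the comparison. The documents give no count and expect very few such women.

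**Conclusion.** The inconsistency is real and sits in the co-primary derivation. For women stopping at about Day 12 to 27 with adequate diaries, the SAP applies a composite strategy under a while-on-treatment label and does not declare the departure from Protocol 13.5.2. For women stopping sooner, it prescribes both non-response and exclusion. It would go too far to infer that the co-primary analysis as a whole misses its estimand: women who discontinue from Day 28 up to Month 3 are still assessed while on treatment.

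The size is probably small. The shift of 0.3 to 3.7 points is an upper figure resting wholly on assumed stopping and response rates. NMPP power stays at 97.0% to 98.4% if 2% to 10% of both arms are affected, and among the splits examined it falls below 95% only at 2% placebo vs 10% active (93.9%). The case for correction is a coherent estimand and a reproducible primary result; the trial's power is not in doubt.

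**What to change.** State one rule and use it in SAP 4.2.8.1, 4.6.2, 4.6.3 and 4.6.4:

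- Score available on-treatment days when the 12-entry minimum is met, as in Protocol 13.5.2 and the stated estimand. Say explicitly that the minimum is a count of 12 entries also when the window is shorter than 28 days.
- Treat women treated under 28 days who do not meet the minimum as non-responders, with zero change on numeric endpoints, as in Protocol 13.5.8. State that this takes precedence over the exclusion sentence in 4.6.2.1.2 and its counterpart in 4.6.3.
- Keep the current rule, under which everyone treated for less than 28 days is a non-responder, as a sensitivity analysis.
- List the change in section 5, and report by arm how many women were treated under 28 days and how many of them met the minimum.

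The cost is SAP wording, one derivation flag and one repeated model per endpoint. SAP 4.3 allows unblinded Month 6 results to reach the sponsor once the Month 6 thresholds are in the SAP, and they now are. If the co-primary has already been run, report both derivations and say which was specified first.
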